5.6.1.1. Laboratory: Collection of Blood and Urine Specimens

Biochemical measures to be obtained are listed in Table 5-1.

Laboratory specimens must be obtained under conditions of metabolic stability, defined as no DKA during the previous month, except for diabetes autoantibodies that can be collected at any time after initial diagnosis

Stimulated C-peptide (mixed meal challenge): Selected Patients 8 years of age or older at the time of their baseline In-Person Visit will be invited to have a stimulated C-peptide test. A fasting C-peptide and HbA_{1c} will be obtained. Following a mixed meal (Boost) challenge, C-peptide samples will be drawn at designated intervals consistent with current science. The stimulated C-peptide test will be used as follows:

- a. To establish criterion measures for insulin production among Patients with biochemically defined diabetes. This age cut-point was selected because of potentially increased difficulty to clinically diagnose type 1 versus type 2 (or hybrid) diabetes in youth at or beyond the early pubertal stage. Furthermore, based on prior work, it is expected that almost all type 2 patients will be at least 8 years of age. Detail on the use of this information is provided in Section 7 – Typology.
- b. To observe the natural history of insulin production among type 2 diabetes cases.
- c. To observe insulin production among Patients whose diabetes type is unknown according to baseline SEARCH data collection efforts. Criterion measures will be applied to these Patients (see Section - Typology).

- d. To observe the natural history of insulin production among all incident cases and prevalent cases with hybrid diabetes.
- e. To assess insulin production in both incident and prevalent cases with previously known genetic beta cell defects.

Sample storage (repository). With the appropriate process of obtaining informed consent in accordance with local IRB requirements, biologic samples will be stored for future analyses, pending acquisition of the necessary funding. See Section 11 - Human Subjects - for further description of the sample repository.

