5.13. SUMMARY OF MEASURES

Table 5-2 summarizes the measures to be taken over time for the SEARCH cohort. Note, the type of case generally will not be known until the baseline data are collected.

Table 5-2. Summary of Data Collection Measure Time Points

		Year of Data Collection	
Case Type	Data Element	Baseline	FU Year 1
INCIDENT (Except known beta cell and other diabetes types of diabetes – see below)	Initial Patient Survey	X	
	In-Person, Physical Exam	X	X
	In-Person, Questionnaires	X	X
	In-Person Lab		
	DAA	X	X
	Glucose, HbA1c, lipids	X	X
	Urine albumin & creatinine	X	X
	Storage	X	X

Case Type	Data Element	Year of Data Collection		
		Baseline	FU Year 1	
	Fasting C-peptide (< 8 years old at baseline)	X	X	
	Stimulated C-peptide (\geq 8 years old)	X	X	
	Medical Record Review/ Clinical Presentation & Utilization	X		
PREVALENT (Except known beta cell and other diabetes types of diabetes – see below)	Initial Patient Survey	X		
	In-Person, Physical Exam	X		
	In-Person, Questionnaires	X		
	In-Person, Lab			
	DAA	X		
	Glucose, HbA1c, lipids	X		
	Urine alb. & creatinine	X		
	Storage	X		
	Fasting C-peptide	X		
Follow-up Mailed Questionnaire		X		
KNOWN GENETIC B-CELL DEFECT (Incident or Prevalent)	Initial Patient Survey	X		
	In-Person, Physical Exam	X		
	In-Person, Questionnaires	X	X	
	In-Person Lab			
	DAA	X	X	
	Glucose, HbA1c, lipids	X		
	Urine albumin & creatinine	X		
	Storage	X	X	
	Fasting C-peptide (< 8 years old at baseline)	X	X	
	Stimulated C-peptide (\geq 8 years old at baseline)	X	X	
Medical Record/Core Review*	X			
OTHER DIABETES TYPES	Initial Patient Survey	X		
	Follow-up Mailed Questionnaire		X	

* This medical record review will be done for incident cases only.

Hybrid diabetes is diabetes with biochemical features of both type 1 and type 2 diabetes.

Other diabetes types refer to diabetes with a known cause such as steroid-induced diabetes – See Appendix VI for greater detail.

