7.3. DEFINITIONS OF TERMS USED FOR TYPOLOGY

7.3.1. **Type 1 diabetes**

The progressive destruction of the beta cells leading to an absolute deficiency of insulin (see insulinopenia below) that results in diabetes.

Type 1 diabetes will be established if all diabetes autoantibodies (DAA – see autoimmunity below) are negative and any of the following are present:

- a. Fasting C-peptide < 0.8 ng/ml;

Or

- b. Diagnosis of diabetes was made when the subject was < 10 years of age with a weight < the 25th percentile for chronological age or BMI < 50th percentile for chronological age;

Or

- c. Duration of diabetes > 1 year and if daily administration of insulin is stopped it results in DKA.

7.3.2. **Type 1A diabetes (general)**

The autoimmune destruction of the beta cells leading to an absolute deficiency of insulin resulting in diabetes.

7.3.3. **Type 1A diabetes (biochemical)**

The presence, in plasma, of any specific diabetes autoantibody and a fasting C-peptide < 3.7 ng/ml. These markers include antibodies to glutamic acid decarboxylase (GAD), IA-2, and insulin autoantibodies (IAA) measured by radioassay and cytoplasmic islet cell antibodies measured by immunofluorescence (ICA). The frequency of the presence of immune markers decreases with increased duration of disease with only 65% of Type 1A patients having one or more positive immune markers with duration of disease of 10 years^{33,34}.

7.3.4. **Type 2 diabetes (general)**

The presence of insulin resistance (see insulin resistance) and beta cell dysfunction resulting in diabetes. Type 2 diabetes will be established if one of the following exists:

- a. Duration of diabetes > 1 year and no insulin therapy for > 1 month without an episode of diabetic ketoacidosis

Or

- b. Duration of diabetes > 6 months and never treated with insulin.

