7.4.2. Incident algorithms

The incident algorithm will be used to establish type of diabetes for incident cases. This algorithm displays use of data collected from the In-Person Visit Module. For incident cases for whom the In-Person Visit is not available, typology will proceed using data collected from the Medical Record Module or the Core Form. (See Data Collection, Section 5, for descriptions)

Algorithm - Incident cases– Information Available from In-Person Visit

- a. Type 1A diabetes will be established if any of the three DAA (GAD, IAA, and IA-2) is positive and the fasting C-peptide is < 3.7 ng/ml.
- b. Type 2 diabetes will be established if the DAA titers are all negative and the fasting C-peptide is ≥ 3.7 ng/ml.
- c. Hybrid diabetes is established if any DAA are positive and fasting C-peptide is ≥ 3.7 ng/ml.
- d. DAA negative participants ≥ 8 years of age at their baseline examination who have a fasting C-peptide concentration < 3.7 ng/ml will undergo additional DAA and SCP testing as described in Section 5 – Data Collection. These data will be used to classify participants in the following manner.
 - i. If any subsequent DAA become positive, a classification of ‘type 1A diabetes’ will be made.
 - ii. If all subsequent DAA remain negative and one or more fasting C-peptide concentrations < 3.7 ng/ml, classification will be made in the following manner. Clinical characteristics and SCP data collected over time will be compared to the same data generated in the sub-group of the incident cases classified as type 1A or all incident cases classified as type 2 diabetes. Where the data matches these groups, a classification of type 1 or type 2 will be made.
 - iii. In remaining participants who cannot be classified by the method described in ‘ii’ (above), clinical definitions of the types of diabetes found in appendix VI will be used to classify participants as type 1 and type 2 diabetes.

- iv. The remaining participants who cannot be classified by the method described in 'iii' (above) will be classified as untypeable.

Algorithm - Incident cases – Information from In-Person Visit Not Available

Among incident cases for which the In-person Module is not available, information may be available from the Core Form and/or Medical Record review. The following information will be obtained: 1) DAA and plasma C-peptide tests and the laboratory at which these tests were performed, and 2) limited clinical data.

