7.4.3. Prevalent algorithms

The prevalent algorithm is used to establish the type of diabetes for prevalent cases. This algorithm displays use of data collected from the In-Person Visit Module. For prevalent cases for whom the In-Person Visit is not available, typology will proceed using data collected from the Core Form. (See Data Collection, Section 5, for descriptions)

Algorithm - Prevalent Cases – Information Available from In-Person Visit

[figure not shown]
- a. Type 1A diabetes will be established if any of the three DAA (GAD, IAA, and IA-2) are positive and a fasting C-peptide < 0.8 ng/ml (see appendix VII).
- b. Type 1 diabetes will be established if all DAA are negative and a fasting C-peptide < 0.8 ng/ml;
- c. Type 2 diabetes will be established if *all* DAA titers are negative and a fasting C-peptide is ≥ 3.7 ng/ml.
- d. Hybrid diabetes is established if any DAA is positive and fasting C-peptide ≥ 3.7 ng/ml.
- e. DAA positive patients ≥ 8 years of age at their baseline examination who have a fasting C-peptide ≥ 0.8 ng/ml and < 3.7 ng/ml will undergo a single SCP test. These data will be used to type the participants in the following manner:
 - i. The clinical and SCP data will be compared to the same data generated in the sub-groups of the incident cases classified as type 1A, hybrid diabetes and type 2.

[figure not shown]
- ii. The clinical and SCP data will be compared to the same data generated in the prevalent cases classified as hybrid diabetes and prevalent cases that are untypeable.
- f. DAA negative patients ≥ 8 years of age at their baseline examination who have a fasting C-peptide ≥ 0.8 ng/ml and < 3.7 ng/ml will undergo a single SCP test. These data will be used to type the participants in the following manner:
- i. The SCP data will be compared to the same data generated in the sub-groups of the incident cases classified as type 1A diabetes and type 2 diabetes. When the data is comparable to the sub-groups, a classification of type 1 or type 2 will be made.
 - ii. In the remaining participants who cannot be classified by the method described in ‘i’ (above), the clinical definitions of the types of diabetes found in appendix VI will be used to classify participants as type 1 and type 2 diabetes.
 - iii. The remaining participants who cannot be classified by the method described in ‘ii’ (above) will be classified as untypeable.

Algorithm- Prevalent cases – Information Available from In-Person Visit Not Available

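### The written incident algorithm (7.4.2) has no outcome for antibody-negative children under 8 with fasting C-peptide below 3.7 ng/ml, and omits the below-0.8 type 1 rule of 7.3.1(a) and 7.4.3(b)

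*Protocol*

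**What the plan says.** Section 7.4.2 types incident cases with in-person data in four steps. The first three have no age limit:

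- Step a: a positive antibody together with C-peptide below 3.7 ng/ml gives type 1A.
- Step b: "Type 2 diabetes will be established if the DAA titers are all negative and the fasting C-peptide is ≥ 3.7 ng/ml".
- Step c: "Hybrid diabetes is established if any DAA are positive and fasting C-peptide is ≥ 3.7 ng/ml".

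Step d sends "DAA negative participants ≥ 8 years of age at their baseline examination who have a fasting C-peptide concentration < 3.7 ng/ml" to further antibody and stimulated C-peptide testing. Four sub-steps hang from it: a later positive antibody gives type 1A (i); comparison with already typed incident groups gives type 1 or 2 (ii); the Appendix VI clinical definitions come next (iii); whoever is left is untypeable (iv).

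Elsewhere the protocol has a rule for antibody-negative type 1. Section 7.3.1 opens it with "Type 1 diabetes will be established if all diabetes autoantibodies" and requires negative results plus any one of three criteria. The first, 7.3.1(a), is fasting C-peptide below 0.8 ng/ml, with no age limit. Prevalent step 7.4.3(b) repeats it: "Type 1 diabetes will be established if all DAA are negative and a fasting C-peptide < 0.8 ng/ml".

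The age-8 cut-point belongs to the stimulated C-peptide test. Section 5.6.1.1 supports it partly on the ground that "it is expected that almost all type 2 patients will be at least 8 years of age". For younger incident cases Table 5-2 has the row that opens "Fasting C-peptide (< 8 years old at baseline", marked at baseline and follow-up year 1. Antibodies are marked at both times too.

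**The concern.** Type-specific incidence by age is primary aim (a), and section 8.1.1 plans estimates by type down to single years of age. An algorithm that feeds those estimates should give every combination of its inputs an outcome, even if that outcome is untypeable.

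The omission has a direction. For an antibody-negative child under 8, the only result 7.4.2 can reach is type 2, through step b. Yet the protocol expects very little type 2 below age 8, so the children left without an outcome are mostly probable type 1. A cut-point chosen for offering a stimulated test has become a cut-point for receiving any type.

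The prevalent and incident rules also disagree about one profile, antibody-negative with C-peptide below 0.8 ng/ml, and no reason is given.

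**Working it through.** **Age band involved.** Expected annual incident cases aged 0-9, summed over the six centers:

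- Type 1 (Table V-4): 33 + 79 + 10 + 33 + 56 + 62 = 273.
- Type 2 (Table V-5): 3 + 9 + 2 + 2 + 3 + 11 = 30.
- Total: 273 + 30 = 303, as in Table 6-2.

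The rate is 303 / 2,533,318 = 1.196 per 10,000 (stated 1.20). The standard error is √303 / 2,533,318 = 0.0687 per 10,000 (stated 0.069). The relative half-width is 1.96 / √303 = 11.26% (stated 11.2%). The plan's figures reproduce apart from rounding. They are for all types, so they do not depend on the typing rule.

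**Coverage of the written steps.** Crossing antibody status (2) with C-peptide band (3) and age (2) gives 12 cells.

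| Antibodies | C-peptide, ng/ml | Age | Incident, 7.4.2 | Prevalent, 7.4.3 |
|---|---|---|---|---|
| Positive | < 0.8 | < 8 | 1A (a) | 1A (a) |
| Positive | < 0.8 | ≥ 8 | 1A (a) | 1A (a) |
| Positive | 0.8 to < 3.7 | < 8 | 1A (a) | **none** |
| Positive | 0.8 to < 3.7 | ≥ 8 | 1A (a) | step e |
| Positive | ≥ 3.7 | < 8 | hybrid (c) | hybrid (d) |
| Positive | ≥ 3.7 | ≥ 8 | hybrid (c) | hybrid (d) |
| Negative | < 0.8 | < 8 | **none** | type 1 (b) |
| Negative | < 0.8 | ≥ 8 | step d | type 1 (b) |
| Negative | 0.8 to < 3.7 | < 8 | **none** | **none** |
| Negative | 0.8 to < 3.7 | ≥ 8 | step d | step f |
| Negative | ≥ 3.7 | < 8 | type 2 (b) | type 2 (c) |
| Negative | ≥ 3.7 | ≥ 8 | type 2 (b) | type 2 (c) |

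The incident algorithm leaves two cells empty, both antibody-negative and under 8. The prevalent algorithm types the first of these as type 1. It leaves the second empty, along with the antibody-positive under-8 cell in the same C-peptide band. At age 8 or older and below 0.8 ng/ml, the incident case goes to step d, which can end in type 1A, type 1, type 2 or untypeable; the prevalent case is type 1 at once.

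**Can the effect be sized?** If untyped children were left out of the type 1 numerator, the annual shortfall at ages 0-9 would be 273 × s × p × (1 − r). Here s is the share of those cases under 8, p the share of these that are antibody-negative with C-peptide below 3.7, and r the share typed by another section. The protocol gives none of s, p or r. Its one antibody frequency (65% with at least one positive marker, section 7.3.3) is for 10 years' duration and does not apply at onset. No estimate follows.

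**The case against.** The strongest reply is that 7.4.2 is not the only typing text. Several routes carry no age-8 limit:

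- 7.3.1(a) makes every antibody-negative child below 0.8 ng/ml type 1.
- 7.3.1(b) and Appendix VI give type 1 for onset before age 10 with weight below the 25th or BMI below the 50th percentile.
- 7.4.1 falls back on clinical definitions where stimulated C-peptide does not classify.
- 7.2(a) promises longitudinal follow-up and reassignment for anyone unclassifiable at first. With the year-1 antibodies in Table 5-2, a later positive result could reasonably be read into step a.

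In addition, 7.4.4 and the figures around 7.4.3 have no visible content in the copy reviewed, so a flow chart may cover these cells. The two algorithms also differ elsewhere (step a uses 3.7 for incident and 0.8 for prevalent cases), and 7.3.10 notes that C-peptide can be normal early in type 1. A difference is not in itself an error.

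Much of this stands as a limit on the consequence. A reader might infer that type 1 incidence in young children is undercounted, or might attach a percentage to it. The document supports neither. That reading needs 7.4.2 to be applied alone and untyped cases to be dropped from the type 1 numerator. Section 8.1.1 does not say how untyped cases are handled, and an analysis plan not shown may do so.

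The reply does not close the gap. The 7.4.1 fallback follows a test that under-8s are not offered, so its application to them is unclear. Appendix VI's clinical type 1 does not contain the below-0.8 rule. A child at 0.8 to below 3.7 ng/ml who stays antibody-negative, at or above both body-size cut-offs, meets no early type 1 criterion, since 7.3.1(c) needs more than a year's duration. Section 7.2(a) gives no rule for this cell. Early normal C-peptide is no reason to omit a rule for values below 0.8. Whatever a diagram shows, the written steps should be complete and agree with it.

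**Conclusion.** The point holds as an internal inconsistency. The written 7.4.2 leaves two of 12 cells without any outcome, and it disagrees with 7.3.1(a) and 7.4.3(b) on antibody-negative cases below 0.8 ng/ml at every age. Different sections would type the same young child differently, and an analyst would have to choose.

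The risk to type 1 incidence in young children is downward, conditional on 7.4.2 being followed literally. Its size is unknown. The band concerned is part of the 273 type 1 cases per year planned at ages 0-9, but the affected fraction cannot be obtained from the protocol. All-type incidence is unaffected, because registration under section 5.4 does not depend on type. The point should be settled before typing is finalized, since it bears on a primary aim and costs little to correct.

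**What to change.** Reconcile 7.4.2 with 7.2(a), 7.3.1, 7.4.1 and 7.4.3(b):

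1. Either bring the 7.3.1(a) rule (all antibodies negative, fasting C-peptide below 0.8 ng/ml, type 1) into 7.4.2 for all ages and restrict step d to 0.8 to below 3.7 ng/ml, or state why incident cases are treated differently. Adding the rule without narrowing step d would put children aged 8 or older below 0.8 ng/ml under two rules at once. Say also what happens if such a case later becomes antibody-positive.
2. For antibody-negative incident children under 8 at 0.8 to below 3.7 ng/ml, open the follow-up antibody, clinical-definition and untypeable steps, using the year-1 antibodies and fasting C-peptide. The stimulated test can stay limited to age 8 or older.
3. In 7.4.3, give under-8s at 0.8 to below 3.7 ng/ml an outcome in step e (antibody-positive) and step f (antibody-negative). For step e, reconcile with 7.3.3, whose type 1A definition runs up to 3.7 ng/ml.
4. Check that any diagrams under 7.4.4 match the revised text.

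The cost is algorithm wording. The incident tests are already in Table 5-2, and the prevalent gaps can be closed with baseline data and the existing definitions, so no visit or blood draw is added.

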Characteristics of 578 youth diagnosed with type 2 diabetes (Table 2) were available from 6 U.S. case series for whites, African Americans and Hispanics, from one registry of type 1 diabetes, and from 3 reports for American Indians and First Nation People. About 94% of the children and adolescents belonged to minority communities. Mean age at diagnosis was close to the age of puberty (approximately 12 to 14 years), except among the Pima Indians, where it was 16 years of age. Only a few cases occurred in children who were younger than 10 years old at diagnosis, and the youngest was a 4-year-old Pima Indian child. The disease is seen more frequently in females than males. Obesity, a family history of diabetes, and acanthosis nigricans were common among cases. Most of the cases were identified because of the presence of glycosuria during urine testing for school, sport, or employment medical examinations. Vaginal moniliasis was a chief complaint in one study and was reported in 24% of girls; weight loss and ketosis were common, and ketoacidosis was also reported. Among Pima Indian youth, both low and high birthweight, maternal diabetes during pregnancy (either gestational or

type 2 diabetes), and bottle-feeding from birth were associated with type 2 diabetes. At diagnosis, insulin and C-peptide concentrations may be elevated, normal or low. Islet cell antibody titers are negative.

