7.3.5. Type 2 diabetes (biochemical)

The presence of diabetes and insulin resistance (C-peptide \geq 3.7 ng/ml) and the absence of autoimmune markers (see autoimmunity) for type 1A diabetes.

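### Incident step d.i assigns type 1A without regard to C-peptide, contradicting the protocol's own type 1A and hybrid definitions; the C-peptide condition in d.ii, as worded, selects nothing

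*Protocol*

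**What the plan says.** Protocol 7.4.2 types incident cases seen in person. Steps a to c use autoantibodies (DAA) and fasting C-peptide with one cut, 3.7 ng/ml:

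- DAA positive and below 3.7 is type 1A (step a).
- DAA negative and 3.7 or more is type 2 (step b).
- The third cell is step c: "Hybrid diabetes is established if any DAA are positive and fasting C-peptide is ≥ 3.7 ng/ml".

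The definitions agree. Section 7.3.3 and Appendix VI make a value below 3.7 part of biochemical type 1A. Section 7.3.5 defines biochemical type 2 as "The presence of diabetes and insulin resistance", with C-peptide at 3.7 or more and no autoimmune markers. Appendix VI describes hybrid as autoimmunity together with insulin resistance.

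Step d handles the remaining cell: DAA-negative cases aged 8 or older at baseline "who have a fasting C-peptide concentration < 3.7 ng/ml will undergo additional DAA and SCP testing". Its sub-steps are:

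- d.i: "If any subsequent DAA become positive, a classification of" type 1A follows. C-peptide is not mentioned.
- d.ii: "If all subsequent DAA remain negative and one or more fasting C-peptide concentrations < 3.7 ng/ml, classification will be made" by comparing clinical and stimulated C-peptide data over time with incident type 1A and type 2 cases. "Where the data matches these groups, a classification of type 1 or type 2 will be made".
- d.iii: the rest are typed by the clinical definitions in Appendix VI, as type 1 or type 2.
- d.iv: whoever is left after d.iii ("above) will be classified as untypeable").

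Section 7.2(a) says in general terms that cases not classifiable at first will be followed, and re-typed if the pathogenesis becomes clear.

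**The concern.** Step d exists to settle, with follow-up data, the cases that baseline biochemistry could not settle. Section 2.2.2 says of youth with type 2 diabetes: "At diagnosis, insulin and C-peptide concentrations may be elevated, normal or low". Some true type 2 cases should therefore enter step d, and the sub-steps need to say what a later C-peptide at or above the cut means. They do not. Step d.i overrides the cut for DAA-positive cases, and d.ii has no outcome that rests on it.

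Incidence by type and classification of type are both primary aims (1.2). The labels are also reused. Incident type 1A and type 2 cases are the reference groups for matching in d.ii and in the prevalent algorithm (7.4.3 e.i and f.i). Incident hybrids are a further reference group in e.i. Section 7.2(b) uses biochemically classified participants to redefine the clinical definitions. A hybrid filed as type 1A is thus lost from one reference group and added to another.

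**Working it through.** No sample size or power figure is involved. The check sets the sub-steps of d against rules a to c.

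**Inputs.** At entry to step d a case is DAA negative, aged 8 or older, with baseline fasting C-peptide below 3.7 (7.4.2 d). Follow-up visits are annual (5.8). Table 5-2 schedules DAA and stimulated C-peptide at the first of them for incident cases aged 8 or older, and 5.6.1.1 says a fasting sample is taken with the stimulated test. Both values needed to apply rules a to c will therefore exist.

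**Outcomes of step d.** d.i gives type 1A; d.ii and d.iii give type 1 or type 2; d.iv gives untypeable. Hybrid is not among them.

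**One follow-up visit, 2 × 2 = 4 patterns:**

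| DAA | Fasting C-peptide | Rules a–c | Step d, baseline value counted in d.ii | Step d, only follow-up values counted |
|---|---|---|---|---|
| − | < 3.7 | none | d.ii to d.iv | d.ii to d.iv |
| + | < 3.7 | type 1A (a) | type 1A | type 1A |
| + | ≥ 3.7 | hybrid (c) | type 1A | type 1A |
| − | ≥ 3.7 | type 2 (b) | d.ii to d.iv: type 1, type 2 or untypeable | outside d.ii; step d names no outcome |

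The third row is a contradiction on either reading. The fourth depends on the reading. As worded, d.ii asks for one or more values below 3.7, and the baseline value is one, so every DAA-negative case passes. If only follow-up values count, the case leaves d.ii and step d does not say where it goes.

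**Two follow-up visits, 4 × 4 = 16 patterns:**

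- 12 have at least one positive DAA, and all become type 1A. In 16 − 9 = 7 of them, at least one visit meets step c.
- 4 are DAA negative throughout. The two mixed series (one value on each side of 3.7) go to d.ii on either reading. The series with both values at 3.7 or more goes to d.ii only if the baseline value counts.

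These are counts of logical patterns, not frequencies.

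**Does the rest of step d recover type 2?** It can. In d.ii the reference type 2 cases are themselves defined by a value of 3.7 or more, so a case that rises to that level may well match them. In d.iii, clinical type 2 requires more than a year's duration with over a month off insulin and no ketoacidosis, or more than six months' duration and never treated with insulin. Clinical type 1 requires onset before age 10 with a low weight or BMI percentile. A continuously insulin-treated case with onset at 10 or later that fails to match meets neither clinical definition and ends as untypeable, although it satisfies step b.

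**The case against.** Steps a to c carry no restriction to baseline; only step d mentions it. With 7.2(a), one may read them as reapplied at follow-up, so that a DAA-negative case whose follow-up values are all 3.7 or more falls under step b. That reading is available and is probably the intention, but 7.2(a) states no threshold and no order of precedence. If steps a to c are reapplied, step c then collides with d.i, so the text still needs reconciling.

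Section 7.4.4 has no content in the copy reviewed, and flow diagrams may be missing from it. A diagram could show how the threshold is reused. It would not remove the conflict between the written d.i and step c.

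Mixed series are a fair point for the other side. The cut marks the upper tail in healthy adolescents (7.3.10), so one high value after a lower one does not prove type 2, and sending such cases to profile matching is defensible. For that reason, typing every case with any single high follow-up value as type 2 is not recommended.

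A reader might infer that a follow-up value of 3.7 or more can never change the type. The documents do not support that: the fasting sample accompanies the stimulated test, and d.ii and d.iii can both return type 2. Nor do they show that type 2 incidence is understated by any given amount. They do not report what share of type 2 cases start below 3.7, what share rise above it, or how many of those would fail to match. The 164 planned type 2 cases per year (Appendix V, Table V-5) are no base for such an estimate, because they include 30 aged 0–9 (3 + 9 + 2 + 2 + 3 + 11), most of whose age range lies below the step d limit.

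**Conclusion.** The d.i part stands on any reading: its type 1A label contradicts 7.3.3, Appendix VI and step c for a case that turns DAA positive with fasting C-peptide at 3.7 or more. It affects only cases that make both changes after a baseline that was negative and below the cut, so it may be uncommon.

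The d.ii part is real but smaller. As worded, its C-peptide condition is met at entry and separates no one, and a DAA-negative case that later meets step b and 7.3.5 is not assured of being typed as type 2. When all follow-up values are 3.7 or more, reapplying step b is a possible reading but an unstated one.

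The size in cases cannot be derived from the protocol, and no figure should be attached. The conclusion rests on the wording of the rules, not on a count. It assumes that the missing content of 7.4.4 does not replace the written sub-steps.

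**What to change.** In 7.4.2, step d:

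1. **d.i:** a later positive DAA gives type 1A only if the concurrent fasting C-peptide is below 3.7 ng/ml, and hybrid if it is 3.7 or more, consistent with steps a and c.
2. **d.ii:** say whether the baseline value counts towards the condition.
3. **d.ii:** state that a case that stays DAA negative and whose follow-up fasting values are all 3.7 or more is typed as type 2 by step b.
4. **d.ii:** keep profile matching for DAA-negative cases with at least one follow-up value below 3.7, or state another explicit rule for mixed values.

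The change costs wording only, with no new visits or tests, since Table 5-2 and 5.6.1.1 already provide both measurements. Some cases will change type between baseline and follow-up, which 7.2(a) already foresees. The rule should be settled before incident cases are used as reference groups for matching.
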